12.1 Analysis sets

The following analyses sets are defined:

The Enrolled Analysis Set (EAS) includes all participants who signed ICF and are assigned participant numbers. This analyses set will be used to summarize disposition of participants and pre-treatment adverse events.

The Full Analysis Set (FAS) comprises all participants who received at least one dose of study treatment in the extension study. This set will serve as the primary analyses set for all efficacy and safety analyses.

The Per-Protocol Set (PPS) is a subset of participants of the FAS with no protocol deviation with impact in the core study or the extension. The list of protocol deviations criteria will be provided in a separate document.

12.2 Participant demographics and other baseline characteristics

Demographic and other baseline data including disease characteristics will be listed and summarized descriptively in all participants for all analyses sets.

Medical history (ocular and non-ocular) will be tabulated by system organ class.

Relevant medications and procedures will be summarized using number and percentage by ATC class and preferred term according to the WHO Drug Reference list dictionary in all sets, and also listed by ocular and non-ocular events. Other relevant baseline information will be listed and summarized with descriptive statistics as appropriate.

12.3 Treatments

The FAS will be used for the analyses described below.

The duration to the treatment exposure will be summarized descriptively by counts and percentage of participants in 4-week, 8-week, 12-week, 16-week and 20-week intervals at each visit. Frequency of selected treatment patterns will be shown.

Percentages of participants who completed the study as per protocol without treatment discontinuation and interruptions will be summarized in all participants up to Week 56, and within the treatment intervals.

Concomitant medications and significant non-drug therapies prior to and after the start of the study treatment will be listed and summarized according to the ATC classification system in all participants up to Week 56.

12.4 Analysis of the primary endpoint(s)/estimand(s)

The primary objectives of the study are:

- To evaluate the extended durability of brolocizumab in a TtC regimen with respect to the duration of treatment intervals up to Week 56
- To evaluate the functional outcomes of brolocizumab in a TtC regimen with respect to average change in BCVA at Week 52 and Week 56, i.e. change from the extension baseline to the average of Week 52 and Week 56

12.4.1 Definition of primary endpoint(s)/estimand(s)

The primary endpoints of the study are:

- Duration of the last interval with no DA up to Week 56
- Change in BCVA from extension baseline at Week 52 and Week 56

Primary estimands along with the sensitivity estimands are in [Table 12-1](#).

Table 12-1 Primary and sensitivity estimands

Endpoint	Estimand	Estimand definition	Analysis set	Data included in analysis	Statistical methods (including missing data strategy)
Duration of last interval with no DA	Primary estimand 1	Duration of the last interval with no DA, i.e. distribution of the last interval with no DA up to Week 56, i.e. proportion of participants in last interval with no DA that is 4/8/12/16/20-week intervals	FAS	*Last interval with no DA up to Week 56	Two-sided 95% Confidence Interval of proportions. If there was DA, the last interval will be shortened by 4 weeks, down to a minimum of 4 weeks

Endpoint	Estimand	Estimand definition	Analysis set	Data included in analysis	Statistical methods (including missing data strategy)
Change in BCVA	Primary estimand 2	Change in BCVA from extension Baseline at Week 52 and Week 56, i.e. the average difference in BCVA from extension Baseline over the period Week 52 through Week 56	FAS	All data collected until the participant discontinued study treatment and started SOC treatment(s) will be included.	Two-sided 95% Confidence Interval obtained from ANCOVA with age at the baseline categories and BCVA at the baseline categories with (LOCF) imputation / replacement for missing data (e.g. data unavailable due to lost to follow-up) / censored data (e.g. data unavailable due to use of alternative anti-VEGF)

Endpoint	Estimand	Estimand definition	Analysis set	Data included in analysis	Statistical methods (including missing data strategy)
Duration of last interval with no DA excluding participants with protocol deviations with impact	Sensitivity estimand 1.1	Duration of the last interval with no DA up to Week 56, i.e. distribution of the last interval with no DA up to Week 56, i.e. proportion of participants in last interval with no DA that is 4/8/12/16/20-week intervals, excluding participants with protocol deviations with impact as per PPS	**PPS	*Last interval with no DA up to Week 56	Two-sided 95% Confidence Interval of proportions. If there was DA, the last interval will be shortened by 4 weeks, down to a minimum of 4 weeks

Endpoint	Estimand	Estimand definition	Analysis set	Data included in analysis	Statistical methods (including missing data strategy)
Change in BCVA excluding participants with protocol deviations with impact	Sensitivity estimand 2.1	Change in BCVA from extension Baseline at Week 52 and Week 56, i.e. the average difference in BCVA from extension Baseline over the period Week 52 through Week 56; excluding participants with protocol deviations with impact as per definition of PPS	**PPS	All data collected until the participant discontinued study treatment and started alternative treatment(s), will be included.	Two-sided 95% Confidence Interval obtained from ANCOVA with age at the baseline categories and BCVA at the baseline categories and with (LOCF) imputation / replacement for missing data (e.g. data unavailable due to lost to follow-up) / censored data (e.g. data unavailable due to use of alternative anti-VEGF).

Endpoint	Estimand	Estimand definition	Analysis set	Data included in analysis	Statistical methods (including missing data strategy)
Duration of last interval with no DA excluding participants with protocol deviations with impact either in the core study or in the extension study	Sensitivity estimand 1.2	Duration of the last interval with no DA up to Week 56, i.e. distribution of the last interval with no DA up to Week 56, i.e. proportion of participants in last interval with no DA that is 4/8/12/16/20-week intervals, excluding participants with protocol deviations with impact either in the core or in the extension as per PPS	**PPS	*Last interval with no DA up to Week 56	Two-sided 95% Confidence Interval of proportions. If there was DA, the last interval will be shortened by 4 weeks, down to a minimum of 4 weeks

Endpoint	Estimand	Estimand definition	Analysis set	Data included in analysis	Statistical methods (including missing data strategy)
Change in BCVA excluding participants with protocol deviations with impact either in the core study, or in the extension study	Sensitivity estimand 2.2	Change in BCVA from extension Baseline at Week 52 and Week 56, i.e. the average difference in BCVA from extension Baseline over the period Week 52 through Week 56; excluding participants with protocol deviations with impact either in the core study or in the extension study as per definition of PPS	**PPS	All data collected until the participant discontinued study treatment and started standard of care (SOC) treatment(s), will be included.	Two-sided 95% Confidence Interval obtained from ANCOVA with age at the baseline categories and BCVA at the baseline categories variables with (LOCF) imputation / replacement for missing data (e.g. data unavailable due to lost to follow-up) / censored data (e.g. data unavailable due to use of alternative anti-VEGF).
Proportion of participants with at least 16-weeks duration of last interval with no disease activity	Sensitivity estimand 1.3	Proportion of participants in last interval with no disease activity that is at least 16-weeks intervals up to Week 56	FAS	*Last interval with no disease activity up to Week 56	Two-sided 95% Confidence Interval of proportions. If there was disease activity, the last interval will be shortened by 4 weeks, down to a minimum of 4 weeks

Endpoint	Estimand	Estimand definition	Analysis set	Data included in analysis	Statistical methods (including missing data strategy)
Change in BCVA	Sensitivity estimand 2.3	Change in BCVA from extension Baseline at Week 52 and Week 56, i.e. the average difference in BCVA from extension Baseline over the period Week 52 through Week 56	FAS	All data collected until the participant discontinued study treatment and started SOC treatment(s) will be included.	Two-sided 95% Confidence Interval obtained based on mixed effects models with age at the baseline categories and BCVA at the baseline categories
Proportion of participants with at least 16-weeks duration of last interval with no disease activity excluding participants with important protocol deviations	Sensitivity estimand 1.4	Proportion of participants in last interval with no disease activity that is at least 16-weeks intervals at Week 56, excluding participants with important protocol deviations as per PPS	PPS**	*Last interval with no disease activity up to Week 56	Two-sided 95% Confidence Interval of proportions. If there was disease activity, the last interval will be shortened by 4 weeks, down to a minimum of 4 weeks

Endpoint	Estimand	Estimand definition	Analysis set	Data included in analysis	Statistical methods (including missing data strategy)
Proportion of participants with at least 16-weeks duration of the last interval with no disease activity excluding participants with important protocol deviations either in the core study or in the extension study	Sensitivity estimand 1.5	Proportion of participants in last interval with no disease activity that is at least 16-weeks intervals, excluding participants with important protocol deviations either in the core or in the extension as per PPS	PPS**	*Last interval with no disease activity up to Week 56	Two-sided 95% Confidence Interval of proportions. If there was disease activity, the last interval will be shortened by 4 weeks, down to a minimum of 4 weeks

*: If the duration of the last interval falls within the following ranges of [q4w, q8w) or [q8w, q12w), [q12w, q16w), [q16w, q20w) or \geq q20w then the floor value of these ranges i.e. q4w, q8w, q12w, q16w, q20w, respectively, will be used for imputation.

** : Patients who take prohibited concomitant medication are already excluded from PPS as taking prohibited medication is considered a deviation with impact.

12.4.2 Statistical model, hypothesis, and method of analysis

The average change in BCVA from extension baseline at Week 52 and Week 56 will be estimated in Analyses of Covariance (ANCOVA) with baseline age categories and baseline BCVA categories. The estimate of BCVA change will be accompanied by 95% CI.

The distribution of the last interval with no DA up to Week 56 will be described based on counts and proportions of participants at 4-week, 8-week, 12-week, 16-week, and 20-week intervals. The proportions will be accompanied by 95% Confidence Intervals (CI).

12.4.3 Handling of remaining intercurrent events of primary estimand

In case of an intercurrent event, i.e. treatment interruption or discontinuation, the treatment interval will be defined as the last interval with no DA. If there was DA at the last interval, the last interval will be shortened by 4 weeks down to a minimum of 4 weeks.

Missing BCVA data due to intercurrent events, i.e. treatment interruption or discontinuation, will be imputed using last observation carried forward (LOCF) method. Observed values from both scheduled and unscheduled visits will be used for the LOCF imputation.

For participants who discontinue treatment but continue in the study, the BCVA data will be censored at the time the participant started Standard of Care treatment in the study eye.

12.4.4 Handling of missing values not related to intercurrent event

In case of a missing visit for reasons other than specified in [Section 12.4.3](#), the treatment interval will be defined as the last interval with no DA. If there was DA at the last interval, the last interval will be shortened by 4 weeks down to a minimum of 4 weeks.

Missing BCVA values for reasons other than specified in [Section 12.4.3](#) will also be imputed using LOCF method.

12.4.5 Sensitivity analyses for primary endpoint/estimand

Sensitivity analyses to examine robustness with respect to protocol deviations will be performed based on the PPS.

Sensitivity analyses will be performed in a subset excluding participants with protocol deviations with impact either in the core study, or in the extension study.

To evaluate robustness of the analyses based on the LOCF method, sensitivity analyses will be performed on the observed data in the FAS and mixed models for repeated measures (MMRM).

Sensitivity estimands in exposed and non-exposed to the urgent safety measures: As a sensitivity analyses, the proportion of participants with at least 16-weeks as the last interval with no disease activity at Week 56 will be estimated in pre- and post- the urgent safety measures were introduced. The estimates of proportions will be accompanied by 95% CI obtained using [Goodman \(1965\)](#). The analyses will be performed FAS and PPS (excluding participants with important protocol deviations in the extension study and either in the core study or in the extension study).

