12.5 Analysis of secondary endpoints/estimands

12.5.1 Efficacy and/or pharmacodynamic endpoint(s)

FAS will be used to analyze durability, functional and anatomical outcomes.

To evaluate the anatomical outcomes of brolocizumab in all patients and per randomized arm in the core study

- Change in CSFT from extension baseline to Week 52 and Week 56
- Number of visits with presence of IRF and/or SRF, and sub-RPE fluid in the central subfield as assessed by SD-OCT at Week 52 and Week 56

To assess the durability of brolocizumab in all patients and/or per randomized arm in the core study

- Duration of the last interval with no DA up to Week 56
- Duration of the maximal intervals with no DA up to Week 56
- Change of the duration of last interval with no DA between extension baseline and Week 56

To assess the functional outcomes of brolocizumab per randomized arm in the core study

- Change in BCVA from extension baseline to Week 52 and Week 56

Counts and proportions for the endpoints describing durability, tolerability and anatomical outcomes (i.e. number of visits with presence of IRF and/or SRF) will be accompanied by two-sided 95% CI inferred based on binomial distribution for each endpoint and two-sided 95% simultaneous CIs inferred using the Goodman method ([Goodman 1965](#)). The Goodman method is used for obtaining simultaneous confidence intervals (might be better than single binomial confidence intervals) for the parameters of a multinomial distribution, for example for a multinomial endpoint (4-week interval, 8-week interval, 12-week interval, 16-week interval, and 20-week interval). These analyses will be performed for all participants.

For the analyses of functional and anatomical outcome (i.e. change in CSFT) the 95% CI will be inferred based on ANOVA analyses.

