2.6.1 Secondary endpoints

The following secondary endpoints evaluate the anatomical outcomes of brolocizumab in all participants and per randomized arm in the core study:

- Summary statistics of average change in CSFT from baseline of the extension study at Week 52 and Week 56 will be provided. In addition, equivalent summaries will be provided for participants who discontinued the study treatment early at the date of the last treatment and 4 weeks after.
- Summary statistics of average change in CSFT from baseline of the core study to Week 52 and Week 56 will be provided.
- Number (%) of patients with presence of IRF and/or SRF and sub-RPE fluid in the central subfield, as assessed by SD-OCT at Week 52 and Week 56 and by the number of visits will be provided. In addition, equivalent summaries will be provided for participants who discontinued the study treatment early at the date of the last treatment and 4 weeks after.

The following secondary endpoints evaluate the durability of brolocizumab in all participants and per randomized arm in the core study:

- Distribution of the duration of the last interval with no disease activity up to Week 56 will be provided.
- Distribution of the duration of the maximal intervals with no disease activity up to Week 56 will be provided.
- Distribution of the change of the duration of last interval with no disease activity between baseline of the extension study and Week 56 will be provided.

The following secondary endpoints evaluate the functional outcomes of brolocizumab per randomized arm in the core study:

- Summary statistics of the average change in BCVA from baseline of the extension study to Week 52 and Week 56 will be provided.

The following secondary endpoints evaluate the functional outcomes of brolocizumab in all participants and per randomized arm in the core study:

- Summary statistics of the change in BCVA from the baseline of the core study by visit will be provided. Boxplots with a trend line and the line plot of LSM (+/-SE) by visit will also be graphed.
- Summary statistics for the average change in BCVA from the baseline of the core study to Week 52 and Week 56 will be provided.

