2.6.2 Statistical hypothesis, model, and method of analysis

Counts and proportions for the endpoints describing durability, tolerability, and anatomical outcomes (i.e., number of visits with presence of IRF and/or SRF) will be accompanied by 2-sided 95% CI inferred based on binomial distribution for each endpoint and 2-sided 95% simultaneous CIs inferred using the Goodman method (Goodman 1965). The Goodman method is used for obtaining simultaneous CIs (better than single binomial CIs) for the parameters of a multinomial distribution, for example for a multinomial endpoint (4-week interval, 8-week interval, 12-week interval, 16-week interval, and 20-week interval). These analyses will be performed for all participants and within the two regimens.

For the analyses of functional and anatomical outcome (i.e., change in CSFT) the 95% CI will be inferred based on ANOVA analyses. The same analysis model as used for change from

baseline in BCVA will be used with the baseline BCVA categories replaced by baseline CSFT categories.

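### Protocol 12.4.5 gives the by-period proportion with an interval of at least 16 weeks a plain 95% CI by the Goodman simultaneous method alone; for a yes/no proportion that is nominally a 97.5% interval

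*Protocol*

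**What the plan says.** Protocol 12.4.5 adds a sensitivity analysis for the urgent safety measures, in which "the proportion of participants with at least 16-weeks as the last interval with no disease activity at Week 56 will be estimated in pre", with a matching estimate for the later period, in the FAS and the PPS. The next sentence fixes the interval: "The estimates of proportions will be accompanied by 95% CI obtained using" Goodman (1965). It mentions no binomial interval, does not call the interval simultaneous, and gives no number of categories.

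Elsewhere the method has a different role. In Protocol 12.5.1, counts and proportions are "accompanied by two-sided 95% CI inferred based on binomial distribution for each endpoint and two-sided 95% simultaneous CIs inferred using the Goodman method", so Goodman comes second and carries the label simultaneous. The Protocol summary and SAP 2.5.2 pair the two intervals in the same way for the interval distribution. SAP 2.6.2 states the method's purpose: "The Goodman method is used for obtaining simultaneous CIs (better than single binomial CIs) for the parameters of a multinomial distribution", with the five treatment intervals as the example.

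SAP 2.5.4 and SAP Table 2-1 contain neither the analysis by period nor the proportion with at least 16 weeks. SAP Section 4 does not list either as dropped. Protocol 12.4.5 is therefore the only specification.

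**The concern.** A participant's last interval either is or is not at least 16 weeks, so each period yields one binomial proportion. A simultaneous method widens every interval so that all cells are covered together with 95% confidence. With two complementary cells there is nothing to protect: an interval that covers the share at 16 weeks or more also covers the share below 16 weeks, by reflection. The adjustment only raises the confidence level above the one stated.

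What is at stake is modest. The label would be wrong, and the extra width would fall on an analysis that already splits about 250 participants into two periods. Because no category count is given, two programmers could also produce different intervals from the same sentence.

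**Working it through.** **Inputs.** Planned enrollment is about 250 (Protocol 12.8). The assumed shares are 12.7% at 16 weeks and 19.4% at 20 weeks (Protocol Table 12-2), so p = 12.7% + 19.4% = 32.1% for at least 16 weeks. The documents give no period sizes; n = 50 to 250 is a range I assume, and n = 125 is an equal split of 250. The Goodman formula is also an assumption: a score interval whose squared multiplier is the chi-square quantile (1 df) at 1 − 0.05/k.

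**The plan's own figures.** Protocol 12.8 gives widths of 8.3% and 9.8% at N = 250. The simple binomial width is 2 × 1.960 × √(p(1 − p)/n):
- 12.7%: 3.92 × √(0.127 × 0.873/250) = 8.25%
- 19.4%: 3.92 × √(0.194 × 0.806/250) = 9.80%

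Both match. Goodman with k = 5 would give 10.9% and 12.8%. The planning widths at N = 250 are therefore single binomial intervals, and no Goodman width is stated anywhere.

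**Multiplier.**
- Ordinary 95% interval: z = 1.960
- k = 2: z = 2.241, ratio 1.144, nominal level 1 − 0.05/2 = 97.5%
- k = 5: z = 2.576, ratio 1.314, nominal level 1 − 0.05/5 = 99%

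**Width at p = 0.321.** The score width is 2z√(p(1 − p)/n + z²/(4n²)) / (1 + z²/n). For n = 125, p(1 − p)/n = 0.2180/125 = 0.001744.
- z = 1.960: 3.92 × √(0.001744 + 0.000061) / 1.0307 = 16.2 points
- z = 2.241: 4.483 × √(0.001744 + 0.000080) / 1.0402 = 18.4 points

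| n per period (assumed) | Wilson 95% | Exact 95% | Goodman, k = 2 | Ratio to Wilson | Ratio to exact |
|---|---|---|---|---|---|
| 50 | 25.1 | 27.2 | 28.4 | 1.13 | 1.04 |
| 100 | 18.0 | 19.1 | 20.5 | 1.14 | 1.08 |
| 125 | 16.2 | 17.0 | 18.4 | 1.14 | 1.08 |
| 250 | 11.5 | 11.9 | 13.1 | 1.14 | 1.10 |

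**Coverage.** Exact binomial coverage at p = 0.321, Goodman k = 2 against Wilson:
- n = 50: 97.8% against 95.2%
- n = 125: 97.3% against 95.6%
- n = 250: 97.5% against 95.1%

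**Five-cell reading.** If the method is run on the five interval categories, it returns one interval for the 16-week cell and one for the 20-week cell, but none for their sum, which is the quantity wanted. Applying the k = 5 multiplier directly to the combined share would give a nominal 99% interval, 21.0 points wide at n = 125. Neither reading yields a 95% interval for the stated proportion.

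**The case against.** **What stands.** The analysis is descriptive. No difference, test or decision rule between periods is planned, and an interval that is too wide cannot create a false claim. The 97.5% depends on a formula and a category count that the documents do not give. The size also depends on the comparator: the documents speak of intervals based on the binomial distribution and never name Wilson. Against an exact interval the excess is 4 to 10%, so the 14% should not be quoted alone.

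**Possible defences of the text.** If joint 95% coverage over the two periods were intended, 97.5% per period would be a reasonable Bonferroni choice (0.975 × 0.975 = 0.951 for independent periods). Protocol 12.4.5 does not say so. One could also carry over the paired intervals of Protocol 12.5.1, but that section concerns secondary endpoints, and 12.4.5 names one method only.

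**Stronger readings that the documents do not support.**
- A reader might infer that the fluid endpoints have the same fault. They do not: SAP 2.6.2 plans a "2-sided 95% CI inferred based on binomial distribution for each endpoint and 2-sided 95% simultaneous CIs inferred using the Goodman method", so the ordinary interval is there and the other is correctly labelled. The protocol endpoint is "Number of visits with presence of IRF and/or SRF, and sub-RPE fluid in the central subfield as assessed by SD-OCT at Week 52", with Week 56 as the second visit: a count of 0, 1 or 2 with three categories. Only the presence of fluid at a single visit, in SAP 2.6.1, is yes/no; there Goodman is redundant, not misleading.
- A reader might take the SAP's remark that Goodman is better than single binomial intervals as a claim about binary endpoints. The sentence limits it to multinomial parameters.
- A reader might conclude that the by-period result cannot be compared with sensitivity estimand 1.3. Protocol Table 12-1 names no interval method for that estimand, so this cannot be established.

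**Conclusion.** The point holds for Protocol 12.4.5 only, and it is minor. A simultaneous multinomial method is the sole interval for a single yes/no proportion and carries a plain 95% label. Under the standard alpha/k formula with k = 2 the nominal level is 97.5%. At p = 32.1% and n = 50 to 250, the interval is 13 to 14% wider than Wilson and 4 to 10% wider than exact binomial. At an assumed 125 per period the excess is 2.2 points over Wilson (18.41 − 16.16 = 2.25 before rounding) and 1.4 over exact (18.41 − 17.01).

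The conclusion rests on the assumed formula and on assumed period sizes. The misfit between a multinomial method and a single proportion does not depend on either. The error is conservative, affects no primary result, and sits in an analysis that only the protocol specifies.

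**What to change.** In Protocol 12.4.5, replace Goodman with a named single-proportion 95% interval, Wilson or exact binomial, for each period. If joint coverage over the two periods is wanted, say so and state the level per period. Keep Goodman for the multi-category interval distribution, where it is reported as simultaneous beside the binomial interval, and state the number of categories.

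The text change is one line. SAP 2.5.2 plans binomial intervals for the five separate interval categories, not for the combined share by period, so the new interval is not yet among the planned outputs. Programming it is a small task. If the analysis is to be run, SAP 2.5.4 should carry it with the same interval; if it has been dropped, SAP Section 4 should say so.
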